## **1. ABSTRACT**

It is well recognized that breast cancer patients experience significant symptoms during chemotherapy, including anxiety, nausea and vomiting, and appetite loss. Management of the multiple symptoms patients experience typically requires an array of pharmacologic interventions, but patients still often experience residual symptoms despite aggressive symptom management. Although clinical evidence suggests that acupuncture is an effective therapy for reducing chemotherapy-induced nausea and vomiting, as well as other symptoms such as anxiety, acupuncture generally requires additional appointments and a time commitment which is not feasible for many patients.

Preliminary data suggest that ear acupuncture, a subset of acupuncture that involves stimulation of points on the external ear (ear auricles), could provide relief of symptoms without an added time commitment. However, scientific investigation of ear acupuncture to reduce symptoms burden during chemotherapy infusion in breast cancer patients has not been reported.

We will conduct a single arm, pilot feasibility study of ear acupuncture for breast cancer patients during chemotherapy infusions in the Breast Oncology Center. This study will assess the feasibility of recruiting and retaining breast cancer patients, as well as of administering the ear acupuncture protocol. Additional outcomes will include evaluating the impact of ear acupuncture on symptom burden during infusions and health-related quality of life (QOL).

This study will enroll 26 patients receiving chemotherapy infusion for stage I-III breast cancer, for 3 consecutive chemotherapy cycles. During the first cycle of chemotherapy infusion, participants will receive an educational reading booklet. During cycles 2 and 3 of chemotherapy infusions, participants will receive a standardized ear acupuncture protocol. Measurements will be collected at 4 time points in each chemotherapy cycle: Pre-intervention on the Day 1 of infusions, post-intervention on the Day 1 of infusions, on the day after the chemotherapy infusion (Day 2), and on Day 5. Patient-reported outcomes including Edmonton Symptom Assessment System (ESAS), State-Trait Anxiety Inventory (STAI), The MASCC Antiemesis Tool (MAT), will be collected. Safety data will be measured using NCI-CTCAE v.4.023.

Data collected from this study will provide important data for a future randomized controlled trial to evaluate the efficacy of ear acupuncture in reducing symptom burden during chemotherapy infusion for breast cancer.

## **2. BACKGROUND AND RATIONALE**

Acupuncture has been practiced in Asia and other parts of world for thousands of years. Experimental and clinical evidence over past forty years suggest that acupuncture is effective for various conditions, including pain management. However, the use of acupuncture as a therapy for symptom management in cancer patients during stages of cancer journey presents a completely new challenge. In the past 15 years, emerging clinical evidence, largely from randomized clinical trials, suggests that acupuncture be recommended for symptom relief during cancer treatment. Given these data, the National Comprehensive Cancer Network (NCCN), an alliance of the world's leading cancer centers, has recommended acupuncture in its guidelines for the following conditions: adult cancer pain, chemotherapy-induced nausea and vomiting (CINV), cancer-related fatigue, and palliative care. However, acupuncture generally requires one-to-one service as well as additional appointments and time commitment.

### **2.1 Symptom Burden during Chemotherapy Overview**

Symptom burden is the sum of the severity and impact of symptoms reported by patients with a given disease or treatment. Symptoms can be caused by disease itself as well cancer treatment. Multiple symptoms are additive and can significantly affect functions and quality of life of cancer patients. It is well recognized that breast cancer patients experience a significant number of symptoms during chemotherapy, including anxiety, appetite loss, depression, and pain.

One study found that patients with early stage breast cancer who received chemotherapy experienced significantly more pain, tiredness, depression and diminished well-being compared to those who did not receive chemotherapy. In another study, 13.2% and 21.1% breast cancer patients reported moderate to severe nausea and loss of appetite respectively. Despite the use of advanced antiemetic medications, chemotherapy induced nausea and vomiting (CINV) is still a significant side effect of cancer therapy, particularly delayed nausea. Adriamycin-cyclophosphamide (AC) is a standard chemotherapy regimen for breast cancer patients. With this regimen, one study reported an acute vomiting rate of 15% and delayed nausea rates of 73%-82% during chemotherapy in breast cancer patients. Another study reported that 37% of breast cancer patients had nausea and 13% had vomiting during the first 24 hours of chemotherapy while 70% and 15% developed nausea and vomiting during 2nd to 5th day after chemotherapy.

Anxiety is another common symptom among breast cancer patients. One study of 913 patients with newly-diagnosed breast cancer found that 77% of patients reported anxiety during the 2 years following diagnosis. Another study found that approximately a fourth to over half of breast cancer patients undergoing or who had undergone breast cancer treatment experienced anxiety, particularly during chemotherapy infusions.

## **2.2 Ear Acupuncture and Clinical Trials**

Ear acupuncture (EA) or auricular acupuncture is a subset of acupuncture that involves the stimulation of points on the external ear (ear auricles). Ear acupuncture has been studied for a number of clinical conditions including pain, epilepsy, substance dependence, anxiety, insomnia, and obesity. Ear acupuncture has also been studied for pre-operative and dental procedure-related anxiety. One randomized controlled trial of ear acupuncture in 182 patients undergoing dental procedures demonstrated a significant reduction of state anxiety by 7.3 points in a group that received acupuncture prior to the procedure versus a 3.7 point reduction in the group that did not receive acupuncture.

Ear acupuncture has also been studied for the treatment of chemotherapy-induced nausea and vomiting. A recent published systematic review of 21 randomized clinical trials with 1713 patients revealed that the effect rate of auricular therapy, including ear acupressure and ear acupuncture, for CINV ranges from 44% to 93%. The average sample size of these trials was 81. The majority of these trials used acupressure as the intervention. One study (n=80) evaluated the addition of auricular acupuncture to antiemetic drugs in a breast cancer population and reported. It reported an effective rate (the proportion of grade 0-2 toxicity) of 87.5% in the acupuncture arm versus 45% in the control arm^27, as defined by the World Health Organization (WHO) Recommendations for Grading Acute and Subacute Toxicity. Further study is needed.

In 2016, we piloted an ear acupuncture service for breast cancer patients at DFCI. Our initial data indicated that about 43% of patients reported nausea and 79% of patients reported anxiety during infusion time. Anecdotal reports suggested that patients reported reductions in both nausea and anxiety immediately after receiving an ear acupuncture treatment.

## **2.3 Mechanisms of Ear Acupuncture**

[figure not shown]
The mechanisms of ear acupuncture are believed to be mediated through the autonomic nervous system, specifically through stimulation of auricular branches of the vagus nerve (ABVN) in the outer ear. Figure 1 presents the sensory nerve innovations of external ear. Animal studies found that afferent projections from ABVN to the nucleus of the solitary tract (NTS) form the anatomical basis for the vagal regulation of auricular acupuncture. A so-called “auriculovagal afferent pathway” (AVAP) has been suggested in which both the autonomic and the central nervous system could be modified by auricular vagal stimulation. Another animal study found that auricular vagal stimulation improves burn-induced delay in gastric emptying, possibly mediated via the sympathetic-COX-2 pathway. In addition, auricular stimulation have been found to affect autonomic functions of cardiovascular, respiratory, and gastrointestinal systems. Other factors such as the neuroendocrine system, neuroimmunological factors, neuroinflammation, and neural reflex, as well as antioxidation have also been suggested.

**EACH STUDY: Ear Acupuncture During Chemotherapy Infusion for Breast Cancer, a Feasibility Study Protocol**

General or body acupuncture has been effectively used in clinical practice for CINV and other symptoms, however, given that breast cancer patients are often required to spend hours of infusion time during which patients experience a variety of psychological and physical symptoms, ear acupuncture could provide relief of symptoms without an added time commitment. However, scientific investigation of ear acupuncture to reduce symptoms burden (SB) during chemotherapy infusion in breast cancer patients has not been well-studied.

Figure 1: Sensory nerve innovations of external ear

**Sensory nerve innovations of external ear**

### **3. OBJECTIVES**

1. To evaluate the safety and feasibility of recruiting and retaining breast cancer patients (n = 26), during 3 cycles of adjuvant or neoadjuvant chemotherapy, as measured by rate of recruitment, ear acupuncture compliance, measure collection, and incidences of acupuncture-related side effects during the trial.
2. To collect preliminary efficacy data on ear acupuncture for the reduction of symptom burden (SB) including chemotherapy-induced CINV and anxiety in breast cancer patients, as measured by the *Edmonton Symptom Assessment System (ESAS)*, *State-Trait Anxiety Inventory (STAI)*, the *MASCC Antiemesis Tool (MAT)*, the usage of antinausea medications as well as the ER visits and the hospital admission rate during the trial.

---

 The Multinational Association of Supportive Care in Cancer (MASCC)

## **4. ELIGIBILITY**

### **4.1 Inclusion**

Inclusion Criteria:

1. History of histologically or cytologically proven Stage I-III breast cancer receiving intravenous chemotherapy on an every 14 days or every 21 days schedule
2. Age  $\geq$  18 years
3. Eastern Cooperative Oncology Group (ECOG) performance status of 0 or 1
4. Signed informed consent

### **4.2 Exclusion**

Exclusion Criteria:

1. Receiving weekly chemotherapy
2. Unstable cardiac disease or myocardial infarction within 6 months prior to study entry
3. Uncontrolled seizure disorder
4. Active clinically significant uncontrolled infection
5. Prior use of acupuncture within 3 months prior to the study entry
6. Uncontrolled major psychiatric disorders, such as major depression or psychosis
7. Metastatic breast or other cancer

### **4.3 Inclusion of Women, Minorities and Other Underrepresented Populations**

[figure not shown]
This protocol will be open to women and minorities. Women comprise approximately 98% of the breast cancer patients at Dana-Farber Cancer Institute.

Minorities represent 10-20% of the breast cancer patients at Dana-Farber. Previous trials have demonstrated that 7-25% of patients enrolled on clinical trials are minorities.

## 5. STUDY DESIGN AND PROTOCOL OVERVIEW

This single arm feasibility study will enroll 26 patients receiving chemotherapy for stage I-III breast cancer. Patients will be enrolled into a single ear acupuncture arm for 3 consecutive chemotherapy cycles. During the first cycle of chemotherapy infusion, participants will receive an educational reading booklet (*Chemotherapy and You* by National Center Institute). During cycles 2 and 3 of chemotherapy infusions, participants will receive a standardized ear acupuncture protocol. Each ear acupuncture session lasts for 30 minutes (Figure 1). The study patients will have an option to continue ear acupuncture treatments with their subsequent chemotherapy infusions but no additional data will be collected. Measurements will be collected at 4 time points in each chemotherapy cycle: Pre-infusion on the Day 1 of chemotherapy, post-intervention on the Day 1 of infusions, on the day after the chemotherapy infusion (Day 2), and on Day 5. Patient-reported outcomes including ***Edmonton Symptom Assessment System (ESAS)***, ***State-Trait Anxiety Inventory (STAI)***, ***The MASCC Antiemesis Tool (MAT)***, anti-nausea medication usage and emergency events diary will be collected. Safety data will be measured using NCI-CTCAE v.4.023 (Figure 2). Measures will be compared between chemotherapy cycles.

Figure 2: Study Schema

 The Multinational Association of Supportive Care in Cancer (MASCC)

## **6. SUBJECT RECRUITMENT AND ENROLLMENT**

Patients will be recruited from the Breast Oncology Center at the Dana-Farber Cancer Institute.

We will utilize multiple active recruitment techniques to maximize participation and generalizability. We will use the following strategies to identify potential participants:

- Review of clinic schedules and patient lists for medical oncologists at Dana-Farber Cancer Institute to identify patients with Stage I-III breast cancer who are scheduled to initiate intravenous chemotherapy on every 14 days or every 21 days schedule, such as dose-dense AC followed by paclitaxel regimen or AC followed by paclitaxel with trastuzumab. A HIPAA waiver will be obtained from the DF/HCC IRB to review these patient lists.
- Advertisements in patient areas (see Appendix IX)

For potential participants identified through patient lists, we will contact providers (medical oncologists) and request permission to contact their patients. Providers will be asked to indicate any patients who should not be approached regarding participation in this study. Once potential participants are identified, they will be contacted during a clinic visit or through mailings. For patients with upcoming clinic visits, the research coordinator will approach potential patients in clinic. For patients without an upcoming clinic visit, invitation letters will be mailed with a reply card to indicate interest and an opt-out card (see Appendix VIII). For patients who are self-identified through advertisements in clinic, we will obtain permission from their treating physician before participation in the study.

Interested subjects identified through these recruitment strategies will be screened by the research study staff either in person or by phone initially and if potentially eligible, he or she will schedule a visit with a member of the study staff to review the protocol and sign informed consent.

### **6.1 Registration Procedures**

#### **General Guidelines for DF/HCC Institutions**

Institutions will register eligible participants in the Clinical Trials Management System (CTMS) OnCore. Registrations must occur prior to the initiation of the protocol intervention. Any participant not registered to the protocol before protocol intervention begins will be considered ineligible and registration will be denied.

An investigator will confirm eligibility criteria and a member of the study team will complete the protocol-specific eligibility checklist.

Following registration, participants may begin the protocol intervention. Issues that would cause delays should be discussed with the Overall Principal Investigator (PI). If a participant does not receive the protocol intervention following registration, the participant's registration on the study must be canceled. Registration cancellations must be made in OnCore as soon as possible.

## **6.2 Registration Process for DF/HCC Institutions**

DF/HCC Standard Operating Procedure for Human Subject Research Titled *Subject Protocol Registration* (SOP #: REGIST-101) must be followed.

## **7. SPECIMEN/DATA COLLECTION PROCEDURES**

The pre-infusion assessments will be collected before patients are given educational materials (cycle 1) or receive acupuncture (cycles 2 and 3) on Day 1 of cycles 1-3. The post-intervention assessments will be repeated after the completion of reading educational material or acupuncture on Day 1, Day 2 and Day 5 of cycles 1-3.

Study measures will be collected according to the following schedule (Table 1):

Table 1. Schedule of Study Measures

	Tracking Log	Consent Form	Educational Booklet	ESAS	STAI	MAT	Medication Log	Event Log	AES	Acupuncture Tx Form
Recruitment	X	X					X			
Cycle 1				X	X	X				
Pre-Intervention	Day 1			X						X
Post-Intervention	Day 1			X		X				
	Day 2			X		X				
	Day 5			X		X			X	
Cycle 2				X		X				
Pre-Intervention	Day 1			X		X				X
Post-Intervention	Day 1			X		X				
	Day 2			X		X				
	Day 5			X		X			X	
Cycle 3				X		X				
Pre-Intervention	Day 1			X		X				X
Post-Intervention	Day 1			X		X				
	Day 2			X		X				
	Day 5			X		X			X	

Study measures will be collected by the study CRC (cycle 1) and/or by the study acupuncturists (cycle 2 and 3). The post-acupuncture assessments will be collected by the study acupuncturists. Assessments will be coordinated with ear acupuncture visits when possible, so that patient convenience is maximized. Day 2 and Day 5 assessments will be filled out by the patients at home and returned to the study CRC at the next visit. The home assessments will be put in an envelope to keep the confidentiality. To facilitate completion, patients will be reminded by phone and by email to complete the home assessments. Patients may also choose to complete the home assessments over the phone with the study coordinator.

The following measures will be collected:

### **7.1 The Edmonton Symptom Assessment System (ESAS)**

Our primary outcome is symptom burden (SB) as measured with the Edmonton Symptom Assessment System (ESAS). ESAS is a validated symptom battery that assesses the average intensity of 9 symptoms (pain, fatigue, drowsiness, nausea, appetite, shortness of breath, depression, anxiety, feelings of well-being), each with an 11-point numerical rating scale that ranges from 0 (no symptom) to 10 (worst intensity). In clinical trial settings, symptom burden based on ESAS is generally use the physical score, the emotional score and the total symptoms score. The physical score ranges between 0 and 60, representing the sum of ESAS pain, fatigue, nausea, drowsiness, dyspnea, and loss of appetite. The emotional score consists of both anxiety and depression (total 0-20). The total symptom score represents the combination of physical and emotional scores as well as well-being (total 0-90). Higher scores indicate higher symptom burden. The ESAS is a self-administered questionnaire that was developed and validated to rapidly assesses patients' symptoms burden. The reliability by test-retest with the ESAS and within 1 day is generally high, exceeding 0.8. Correlations between individual ESAS items and scores with other alternative similar tools are good, particularly for physical symptoms. For example, ESAS symptoms correlate strongly with Memorial Symptom Assessment Scales such as shortness of breath (0.85), appetite (0.75), nausea (0.62), nervous (0.45), and depression (0.44). ESAS symptoms correlate strongly with items in the Symptom Distress Scale as well. Correlation with the Brief Pain Inventory and pain was reported to 0.61. ESAS has been used in breast cancer population to assess symptom burden and quality of life. ESAS will be collected 4 times during each cycle.

### **7.2 State-Trait Anxiety Inventory (STAI)**

State-Trait Anxiety Inventory (STAI) is a validated questionnaire measuring the presence and severity of current symptoms of anxiety and a generalized propensity to be anxious. It has 2 subscales: the State Anxiety Scale (S-Anxiety) evaluates the current state of anxiety and the Trait Anxiety Scale (T-Anxiety) evaluates relatively stable aspects of “anxiety proneness,” each having 20 items. The State Anxiety Scale is scored on four levels of anxiety intensity from 1= ‘not at all’ to 4= ‘very much’ and with a sum score between 20 and 80. Higher scores indicate greater anxiety. The State Anxiety Scale has been previously used in several acupuncture trials for anxiety. In our present study, the State Anxiety Scale will be used. STAI will be collected 4 times during each cycle.

### **7.3 The MASCC Antiemesis Tool (MAT)**

The MASCC Antiemesis Tool (MAT) is a validated questionnaire developed by the Multinational Association of Supportive Care in Cancer (MASCC). MAT assesses the domains of nausea and vomiting through the acute and delayed phases of CINV. Each phase is assessed by four items that measure the occurrence of CINV, duration of nausea (10-point scale), and frequency of vomiting (number of episodes). MAT will be collected on Day 2 and Day 5 during each cycle of chemotherapy.

### **7.4 Patient Medication Log**

A patient medication log will be kept and administered to track the usage and dose of support medications as well as dietary supplements. Support medications include, but are not limited to: antiemetics: Compazine (prochlorperazine), Lorazepam (Ativan), Ondansetron (Zofran), Dexamethasone and Metoclopramide (Reglan). Laxatives: Senokot, Colace, or Miralax; opioid analgesics: tramadol and other narcotics; and NSAIDs. Dietary supplements include, but are not limited to: glutamine, glutathione, vitamin E and vitamin B12. Data for the medication log will be collected at each scheduled visit.

### **7.5 Acupuncture Expectancy Scale (AES)**

The AES consists of four items measuring the expectation of improvement of illness (symptom), enhanced coping, increased vitality, and symptom alleviation due to acupuncture therapy. Patients are asked to endorse their expectancy of acupuncture for specific symptoms (e.g., joint pain for breast cancer survivors, and fatigue for patients undergoing radiation therapy). Subjects are asked to rate from 1 to 5 on a five-point Likert scale, with 1 indicating “Not at all agree” and 5 indicating “Completely agree” with the expected improvement as result of acupuncture. Possible scores range from 4 to 20, with higher scores indicating greater expectancy. The AES has been validated with an acceptable reliability coefficient. Additionally, the score on the AES was positively correlated with both the perceived effectiveness of acupuncture treatment and the confidence in acupuncture care. The AES will be administered once before the randomization process.

### **7.6 Acupuncture Treatment Form**

An acupuncture treatment form will be generated by the treating acupuncturist at each ear acupuncture treatment. The form will document the following items: acupuncture points used, patient-reported acupuncture intensity, and any acupuncture-related adverse events.

## **8. ACUPUNCTURE PROCEDURE**

All treatments will take place at DFCI and be administered by experienced, licensed and credentialed staff oncology acupuncturists who have also been specifically trained to administer this study protocol. All acupuncture staff members have a minimum of 10 years of experience. The study PI, [name] will train all acupuncturists and periodically observe the treatment technique being performed to ensure the quality of the treatment.

### **8.1 Ear Acupuncture Protocol**

At the infusion during the 1st cycle, the study patients will receive an educational booklet developed by National Cancer Institute. This booklet includes facts about chemotherapy and its side effects. It highlights ways that a patient can care for herself before, during, and after treatment. No acupuncture will be performed during the first infusion cycle. The patient will be encouraged to read the booklet during the infusion. During the second and third infusion cycles, the study patients will receive a 30-minute session of a standardized ear acupuncture treatment.

At each visit, the study patient will be sitting in an infusion chair either reading the booklet (cycle 1) or receiving ear acupuncture treatment (cycles 2 and 3). For each ear acupuncture session, the patient will have ear acupuncture therapy administered to each ear. After the skin of the ear is cleaned with alcohol, six acupuncture needles (SEIRIN®, No. 1., 30 mm x 0.16 mm) will be inserted into acupuncture points bilaterally. The depth of needle insertions is around 2-3 millimeters. Then, acupuncture needles will be gently manipulated to increase stimulation. The patient will be asked to orally report the needling intensity level on a scale from 0-10 (0 being feeling nothing at all and 10 being the strongest one can imagine). Then, the needles will remain in the sites for 30 minutes while receiving IV infusion. After 30 minutes, another round of gentle manual manipulation will be performed prior to the removal of the needles. Figure 3 and Table 2 presents the names and locations of ear acupuncture points.

If a study patient misses an acupuncture treatment, the patient will be asked to make up the missed treatment session during the next chemotherapy infusion, so that a total of 2 consecutive sessions of acupuncture will be provided. The total number of acupuncture sessions received will be recorded for each participant. Any side effects related to the acupuncture will be collected by treating acupuncturists.

An outline of the acupuncture protocol and a summary of acupuncture points to be used are presented below in Figure 3 and Table 2, respectively.

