### **10.2 Endpoints**

Enrolled patients will receive an educational reading material during the first cycle of chemotherapy and ear acupuncture during cycles 2 and 3. The primary feasibility endpoint consists of three parts. The intervention will be deemed feasible if: (a) at least 20 patients (80%) are enrolled by September 2017; (b) all 20 patients complete at least 75% of the acupuncture sessions; and (c) all 20 patients complete at least 9 out of 12 (75%) assessments. Secondary endpoints will investigate changes in patient-reported outcomes relative to baseline (T1) for the following time points: after the intervention (T2), Day 2, and Day 5 after chemotherapy infusion (T3 and T4). Changes will be compared between cycle 1 (no acupuncture) and cycles 2 and 3 (acupuncture).

For the secondary endpoints, we are primarily interested in the effect of acupuncture therapy compared with no acupuncture; therefore, comparisons will be based on the

averages of the assessment change scores over a time interval during acupuncture (cycles 2 and 3) compared with the change during the same time interval of cycle 1.

For example, if  $T_{ij}$  is the score at time  $i$  ( $i = 1$  to 4) during cycle  $j$  ( $j = 1$  to 3), then three pairwise differences will be of interest:

PD1: Change between  $T_2$  and baseline:  $[(T_{22} - T_{12}) + (T_{23} - T_{13})]/2$  vs.  $(T_{21} - T_{11})$

PD2: Change between  $T_3$  and baseline:  $[(T_{32} - T_{12}) + (T_{33} - T_{13})]/2$  vs.  $(T_{31} - T_{11})$

PD3: Change between  $T_4$  and baseline:  $[(T_{42} - T_{12}) + (T_{43} - T_{13})]/2$  vs.  $(T_{41} - T_{11})$

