### **10.3 Sample Size**

Sample size considerations for the secondary endpoints are based on a one-sample t-tests, 80% power, and an overall type-I error of 0.1 (two-sided), which will be divided equally between the three pairwise comparisons (0.033 for each). The detectable effect size based on these operating characteristics is 0.625.

For our main secondary endpoint of ESAS Total Score, it has been reported that the minimal clinically important difference (MCID) for improvement, based on within-patient change, is 5.7 points ( $SD=11.6$ ,  $N=105$ ). For the purposes of this protocol, a clinically significant improvement in ESAS Total Score will be defined as a 6-point decrease.

If the within-patient correlation of change scores between  $T_2$  and baseline is 0.6, then the estimated standard deviation of the pairwise difference (PD1, above) would be 9.4.

There would be 80% power to detect a difference in change scores of 5.9 points. The table following summarizes detectable differences in ESAS Total Score for varying within-patient correlations.

Detectable Differences in ESAS Total Score based on one-sample t-tests, two-sided alpha = 0.033, and 80% power

Within-patient Correlation	Estimated Standard Deviation	Detectable Difference
0.6	9.4	5.9
0.7	8.3	5.2
0.8	7.0	4.4
0.85	6.3	3.9
0.9	5.5	3.4

Therefore, for a sample of 26 patients, we would have at least 80% power to detect the ESAS Total Score MCID, for within-patient correlations of at least 0.6.

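### Does a missed acupuncture session made up at a later infusion spoil the comparison of cycles 2 and 3 with cycle 1?

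*Combined protocol and SAP*

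**What the plan says.** Section 8.1 places ear acupuncture in cycles 2 and 3. After a missed session, "the patient will be asked to make up the missed treatment session during the next chemotherapy infusion". The same sentence gives the purpose of this rule: "so that a total of 2 consecutive sessions of acupuncture will be provided". Each patient's count of sessions received is recorded. Section 7.6 and Appendix V provide a dated form for every session given.

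Section 7 takes the pre-intervention assessment on Day 1 and repeats the measures "after the completion of reading educational material or acupuncture on Day 1, Day 2 and Day 5 of cycles 1-3". Table 1 has no row after cycle 3. Section 7 adds: "Assessments will be coordinated with ear acupuncture visits when possible, so that patient convenience is maximized". Section 5 allows patients to go on with acupuncture at later infusions, without further data collection.

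Section 10.2 states the secondary aim: "we are primarily interested in the effect of acupuncture therapy compared with no acupuncture". The comparison uses the "averages of the assessment change scores over a time interval during acupuncture (cycles 2 and 3") against the change over the same interval in cycle 1. The cycle index runs from 1 to 3. Nothing is said about a cycle whose session was missed. Criterion (b) of the primary feasibility endpoint requires that "all 20 patients complete at least 75% of the acupuncture sessions".

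**The concern.** Suppose the infusion goes ahead but the acupuncture does not. Cycle 3 already has its own session, so reaching two sessions implies a further infusion after cycle 3. That is an inference; the protocol names no fourth cycle. Three consequences seem to follow.

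- The Day 2 and Day 5 forms are completed at home, so they can exist for the untreated cycle. PD2 and PD3 would then average one treated and one untreated cycle under the label of acupuncture.
- The Day 1 post-intervention score (T2) is tied to completing acupuncture and is collected by the acupuncturist. For PD1 it is more likely to be missing than diluted.
- The session given after cycle 3 has no scheduled questionnaire, and answers not collected then cannot be recovered.

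At stake would be a secondary estimate biased toward no effect and carried into the planning of the later randomized trial. Two wording points go with this. Section 10.2 does not say whether a made-up session counts toward criterion (b), where 75% of two sessions means both. And a cycle 3 session made up later would not be consecutive with the one in cycle 2.

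**Working it through.** **Inputs from Section 10.3:** n = 26; one-sample t-test; two-sided alpha 0.1/3 = 0.033 per comparison; 80% power; SD of change 11.6; a 6-point decrease as clinically significant; and, at correlation 0.6, "the estimated standard deviation of the pairwise difference (PD1, above) would be 9.4".

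**Assumptions, not in the documents:** k of 26 patients miss one session, with k from 0 to 8; no effect in the untreated cycle, no carry-over and no period effect; the PD1 standard deviation also applies to PD2 and PD3.

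**Step 1. The plan's own figures.** The formula 11.6 × √(1.5 − √2 × r) gives 9.36, 8.28, 7.04, 6.33 and 5.53 for r = 0.6, 0.7, 0.8, 0.85 and 0.9, which matches the table. The form of the expression treats cycles 2 and 3 as uncorrelated. The whole column supports that reading. The 9.4 alone does not settle it, because correlation 0.6 with cycle 1 and about 0.70 between cycles 2 and 3 gives nearly the same value. The exact detectable effect size at n = 26 is 0.610. The stated 0.625 is the value for n = 25 (0.624), so it is slightly conservative. Nothing here needs correcting.

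**Step 2. Dilution under the literal reading.** An affected patient's expected PD is (6 + 0)/2 = 3 points. With f = k/26, the mean is 6 × (1 − f/2) and the variance is SD² + 9f(1 − f). For k = 2 and SD 9.4 the mean is 6 × (1 − 1/26) = 5.77, the SD is 9.43, and noncentral-t power is 0.802.

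| Patients affected (assumed) | 0 | 1 | 2 | 3 | 5 | 8 |
|---|---|---|---|---|---|---|
| Power, SD 9.4 | 84% | 82% | 80% | 78% | 74% | 68% |
| Power, SD 8.3 | 92% | 91% | 89% | 88% | 85% | 79% |
| Power, SD 7.0 | 98% | 97% | 97% | 96% | 94% | 91% |

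The 80% target survives 2 affected patients at SD 9.4, the least favourable row of the plan's table, and 7 at SD 8.3. Carry-over of 25% or 50% into a missed cycle 3 would raise the affected patient's expected PD to 3.75 or 4.5, so the dilution would be smaller.

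**Step 3. PD1 if T2 is missing.** Dropping 2, 3, 5 or 8 patients leaves n = 24, 23, 21 or 18. At SD 9.4 and 6 points, power is 80%, 78%, 74% (0.735) and 66% (0.655).

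**Step 4. What a delivered-cycle analysis would gain.** Affected patients contribute only their treated cycle, so the mean returns to 6. Under the table's structure their SD is 11.6 × √(2 − √2 × 0.6) = 12.45, against 9.36 with two cycles. With 2, 5 and 8 affected the average SD is 9.64, 10.03 and 10.41, and power is 0.816, 0.783 and 0.751. By planned cycle it is 0.805, 0.748 and 0.685. The gain with two affected is 0.816 − 0.805 = 0.011. Larger gains need 5 to 8 affected patients, that is 19% to 31% of the sample.

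**The case for a change.** The best case for a change is that the protocol foresees missed sessions and gives an operational rule for them, but no matching rule for data collection or analysis. The stated interest is acupuncture against none, and a cycle without acupuncture does not estimate that. The remedy looks cheap: a few sentences, and questionnaires at the make-up infusion. At SD 9.4, three affected patients already bring power below 80%.

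The mismatch between the sections stands. The case for changing the plan does not, for five reasons.

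- The literal reading is not the only one. If the study cycle and its questionnaires move with the session, no untreated cycle enters PD1 to PD3. No section states this, and none excludes it.
- The trigger is narrow. Acupuncture is given in the infusion chair, so a session is missed in this sense only if the infusion goes ahead without it.
- Section 10.4 already adds model-based analyses of change over time and displays by cycle. These do not commit to modelling actual receipt, but they leave room for it.
- Questionnaires at a make-up infusion have doubtful value. Eligibility does not guarantee a fourth infusion, and the recruitment section describes regimens that change drug partway, so the make-up cycle may not be comparable with cycle 1.
- A delivered-cycle analysis selects on attendance. If patients skip sessions when they feel worse, it drops their worst cycles and can flatter the treatment.

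**Conclusion.** No change to the plan is needed. Keeping the comparison by planned cycle is a sound choice: it avoids selection on attendance, at the price of a modest dilution if sessions are missed. With 1 or 2 of 26 patients affected, a 6-point effect and SD 9.4, power is 82% or 80%; at SD 8.3 it is 91% or 89%. These figures rest on an assumed number of misses and on no carry-over or period effect. A serious loss would take 5 or more affected patients at the plan's lowest correlation.

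What remains is a gap that analysts can fill sensibly. They can report how many patients missed a session and, if that number is not trivial, add a sensitivity analysis limited to the treated cycles, identified from the dated treatment forms. Counting a made-up session toward criterion (b) is the natural reading of Section 8.1. The mismatch between consecutive sessions and a missed cycle 3 session is a matter of wording. The dilution concerns secondary endpoints only, and no stated sample size or power figure is shown to be wrong.
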